## 13.0 Traumatic Audio Script Paradigm

The script-driven imagery procedure is based on previously published fMRI methods [127]. A neutral and a traumatic event will be collected during preparatory session 3 and condensed into an audio recording of 30 seconds. Patient will be asked to rate how distressed they feel (SUDS) after collection of the neutral event and after the collection of the traumatic event. During the paradigm, participants will be instructed to lie still, breathe through his/her nose, and allow themselves to begin focusing on the script, as soon as the audio recording is played. As soon as the participant has heard the script, they will be encouraged to remember all sensations that were associated with the event for approximately 60 seconds. Both the neutral and the traumatic script will be played two times. The total task time is of approximately 14 minutes. The heart rate will be measured during the entire Traumatic Audio Script Paradigm period.

## 14.0 Data Analysis: Traumatic Audio Script Paradigm

Brain activation during the recall of the neutral event will be calculated by using the average activation patterns during the final 30 seconds of each period of recollection of the neutral event. Brain activation during the recall of the traumatic event will be calculated on the basis of the average activation patterns during the final 30 seconds of each period of recollection of the traumatic event. The difference in brain activation between these two conditions will be compared between baseline scan and post-treatment scan.

Functional maps of the activated pixels will be constructed by pixel-by-pixel comparisons of the signal intensity in the baseline and task-related images. Statistical parametric mapping methods (SPM12 software) will be used. Basis functions representing epochs of interest will be entered into SPM12. Variability in scans attributed to each basis function relative to SPM12's implicit baseline will be revealed by using contrasts. Fixed-effects analyses will be performed by modeling each group's evoked blood-oxygen-level-dependent (BOLD) response with hemodynamically convolved boxcar basis functions. The regions of interest will be defined on the basis of T1-weighted images and Talairach coordinates.

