#### **10.0 Emotional Faces Task**

The experimental paradigm during functional MRI scanning consists of a blocked design, including an emotion condition with angry, fearful, sad, happy and neutral face stimuli known to reliably activate the anterior medial temporal lobe including the amygdala [128], and a control condition with scrambled faces. Twenty-four stimuli were selected for each of five facial expressions, comprising 12 female and 12 male faces. Each face will not be presented more than four times. The control condition (scrambled faces) will be presented 80 times. To reduce anticipatory effects, an event-related design was used that involved a pseudo-random presentation of a total of 200 stimuli against a black background. Each photograph will be shown on the screen for 2.5 s, with an interstimulus (black screen) interval varying between 0.5 and 1.5 s. Participants have to indicate each face's gender by pressing one of two buttons with the index finger of the left or right hand on two magnet-compatible button boxes. During the presentation of scrambled faces, participants have to press left or right buttons in conformity with the instruction presented on the screen (*i.e.*, an arrow pointing to the left or to the right). The reaction time will be recorded.

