## 11.0 Data Analysis: Emotional Face-Matching Task

Image analysis will be performed with SPM12 (http://www.fil.ion.ucl.ac.uk/spm). The first five EPI-volumes will be discarded, and the remaining images will be realigned to the first volume. Images will be then co-registered to the anatomical scan, corrected for differences in slice acquisition time, spatially normalized to the MNI T1 template, resampled into  $2 \times 2 \times 2$  mm^3 voxels, and spatially smoothed (8 mm FWHM). Statistical analysis will be performed within the framework of the general linear model. To assess the influence of MDMA-assisted psychotherapy on neural responsivity, the two experimental conditions (posttreatment scan; baseline scan) will be modeled as box-car regressors convolved with the canonical hemodynamic response function of SPM12. In addition, the realignment parameters will be included to

model potential movement artifacts, as well as a constant. Furthermore, a high-pass filter (cut-off 1/128 Hz) will be included, and temporal autocorrelation will be modeled with an AR (1) process. Contrast images subtracting the visuo-motor control condition from the emotion condition will be obtained and analyzed in subsequent random effects models.

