## 12.0 Hypothesis: Emotional Face-Matching Task

We hypothesize that upon completion of the treatment (post-treatment scan vs. baseline scan) participants will display a reduced amygdala response to fearful vs. angry faces.

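### fMRI sub-study (exploratory): the trauma-script analysis names only a fixed-effects group model, and the one face-task contrast specified cannot test the fearful-versus-angry hypothesis

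*Protocol*

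**What the plan says.** All references are to Protocol Appendix A unless stated.

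**Trauma script.** Section 13.0: "Both the neutral and the traumatic script will be played two times". Section 14.0 averages activation over the last 30 seconds of each recall period and sets out the comparison: "The difference in brain activation between these two conditions will be compared between baseline scan and post-treatment scan". It names no model for that comparison. Its second paragraph, on building the maps in SPM12, adds: "Fixed-effects analyses will be performed by modeling each group's evoked blood-oxygen-level-dependent (BOLD) response with hemodynamically convolved boxcar basis functions". Section 15.0 expects lower amygdala and insula activation, higher mPFC and hippocampal activation, and a correlation with SUDS reductions.

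**Face task.** Section 10.0 says the paradigm "consists of a blocked design, including an emotion condition with angry, fearful, sad, happy and neutral face stimuli", with scrambled faces as control. A few lines later it says "an event-related design was used that involved a pseudo-random presentation of a total of 200 stimuli". Section 11.0 says "the two experimental conditions (posttreatment scan; baseline scan) will be modeled as box-car regressors", and then: "Contrast images subtracting the visuo-motor control condition from the emotion condition will be obtained and analyzed in subsequent random effects models". The hypothesis in 12.0 is that "participants will display a reduced amygdala response to fearful vs. angry faces".

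**Status.** Section 5.0 makes the sub-study exploratory and plans to relate fMRI outcomes to CAPS-5 change. Section 6.0 allows later analysis, reported in an addendum. SAP 2.0 promises a separate fMRI SAP. SAP 7.0 describes MP18 as one-arm, with no sample-size calculation.

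**The concern.** **Trauma script.** A fixed-effects group analysis measures the mean change against scan noise alone. If patients differ in how much they change, the standard error is too small, the test rejects too often, and the result describes only the patients scanned. The reference to each group has no counterpart in a one-arm study, and the face task, by contrast, is given random-effects models.

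**Face task.** If the planned contrast does not measure the hypothesised quantity, a positive or a negative result leaves the hypothesis where it was. A fearful-minus-angry contrast added after the data are seen would be a post hoc choice.

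**Wording.** Section 11.0 names the scans, not the stimulus types, as regressors, and 10.0 gives two different designs for one task. An analyst could not build the first-level model from this text without guessing.

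**Working it through.** **Inputs from the documents.** 24 stimuli for each of five expressions and 80 scrambled presentations (10.0): 24 × 5 + 80 = 200, which matches the stated total. Each script is played twice and the final 30 s of each recall is used (13.0, 14.0): 2 × 30 = 60 s per condition per patient per scan. The documents give no alpha, sample size or variance for the sub-study, so these are assumed below.

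**1. Trauma script: false-positive rate under fixed effects.** Let each patient's observed change in (traumatic minus neutral) have between-patient variance τ² and within-patient error variance σ², with r = τ²/σ². The mean over n patients has true variance (τ² + σ²)/n, but a fixed-effects test uses σ²/n. The statistic therefore has variance 1 + r under the null, and

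rate = 2 × [1 − Φ(1.96/√(1 + r))].

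For r = 1: 1.96/√2 = 1.386, giving 0.166.

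| r (assumed) | 0 | 0.1 | 0.25 | 0.5 | 1 | 2 | 4 |
|---|---|---|---|---|---|---|---|
| Fixed-effects rate | 5.0% | 6.2% | 8.0% | 11% | 17% | 26% | 38% |

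The sample size cancels, so more patients do not help. Simulation at r = 1 with assumed n of 8, 12 and 20 gave 0.164, 0.168 and 0.166. A participant-level one-sample t-test on the changes stayed between 0.048 and 0.052 for r = 0.25, 1 and 4 at the same sample sizes.

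**2. Face task: contrast algebra.** Order the conditions as angry, fearful, sad, happy, neutral, scrambled.

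- Specified contrast, expressions pooled equally: E = (0.2, 0.2, 0.2, 0.2, 0.2, −1)
- Hypothesis contrast: F = (−1, 1, 0, 0, 0, 0)
- E·F = −0.2 + 0.2 = 0

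| Change from baseline to post-treatment | E changes by | F changes by |
|---|---|---|
| Fearful −1 only | −0.2 | −1 |
| Angry −1 only | −0.2 | +1 |
| Fearful −1 and angry −1 | −0.4 | 0 |
| Fearful −1 and angry +1 | 0 | −2 |
| All five −1 | −1 | 0 |

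The first two rows give the same value of E for opposite values of F. E therefore does not identify even the direction of F.

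**3. Does the rationale settle which pair was meant?** No. Section 1.0 cites fearful versus happy faces for both the amygdala and the medial prefrontal findings in PTSD, and cites a reduced response to angry faces under MDMA. It does not clearly support fearful versus angry, so the error may lie in 11.0 or in 12.0.

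**4. Precision of the two contrasts.** From stimulus counts alone, the standard error is proportional to √(1/24 + 1/24) = 0.289 for F and √(1/120 + 1/80) = 0.144 for E, a ratio of 2.0. A design simulation used the stated stimulus timing and high-pass filter, with TR, haemodynamic response, autocorrelation and block layouts assumed. It gave 2.0 for a random event-related order, 1.2 to 2.8 for mixed-expression blocks, and a mean of 2.0 (1.1 to 3.1 across orders) for single-expression blocks.

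**The case against.** The best defence is that Appendix A is only a methods outline. A separate fMRI SAP is pending, and that is where the group model and contrasts belong. The fixed-effects sentence sits in the map-construction paragraph beside convolved boxcars, which is the language of within-participant time-series modelling. The planned correlations with SUDS and CAPS-5 change need participant-level values, so the authors may well intend a second stage. For the face task, 11.0 never says that the five expressions are averaged, and separate expression-minus-control images entered in the random-effects models could test 12.0. The error rates reflect assumed variance ratios, and with only 60 s of data per condition per scan the true ratio may be low, where the inflation is about 6% to 8%.

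Some of this stands. That the fixed-effects sentence governs the pre-post test is an inference, the size of the inflation is illustrative, and the face data as collected could support the right contrast. The rest does not answer the point. The sentence speaks of groups, not participants. If it does describe only the first level, 14.0 has no group model at all. The appendix describes one emotion condition holding five expressions and one subtraction, and no per-expression contrast is written anywhere. The pending SAP is the place for the correction and does not show that it has been made.

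**Conclusion.** The point holds and is minor. Section 14.0 names no model for its pre-post comparison, and the only group-level method it gives is fixed-effects. If that method is used for the test, a nominal 5% becomes 5.0% to 38% over assumed variance ratios of 0 to 4, probably towards the lower end. The face-task mismatch needs no variance assumption. It rests only on reading the emotion condition as the pooled five expressions, which is how the text describes it, and on that reading the specified contrast cannot test 12.0. It can still serve the general emotional-faces objective in 5.0. The correlations with CAPS-5 and SUDS do not use the fixed-effects standard error. The primary CAPS-5 analysis and data collection are unaffected.

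**What to change.** Make these changes in Appendix A or the pending fMRI SAP before the data are analysed.

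- **14.0:** estimate traumatic minus neutral for each participant at each scan, test post-treatment minus baseline in a participant-level paired (random-effects) model, and remove the reference to groups.
- **11.0 and 12.0:** either model each expression and test (fearful minus angry) × (post-treatment minus baseline), or restate the hypothesis to match emotion minus control.
- **10.0 and 11.0:** state one design, blocked or event-related, and use the stimulus conditions within each scan as regressors.

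The cost is wording only. Scans and software stay the same, and participant-level values are already needed for the CAPS-5 and SUDS correlations. Some trauma-script p-values will become less favourable. Choosing fearful minus angry will usually mean a noisier contrast, about twice the standard error from stimulus counts and dependent on the design adopted. Restating the hypothesis avoids that loss but gives up the expression-specific claim.

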#### 15.0 Hypothesis: Traumatic Audio Script Paradigm

We hypothesize that upon completion of the treatment (post-treatment scan vs. baseline scan), participants will rate their traumatic script as less emotionally overwhelming and more tolerable to imagine. This will correlate with decreased activation of the amygdala and insula, and increased activation of the mPFC and hippocampus and the strength will correlate with reductions in Subjective Units of Distress (SUDS) ratings.

ICH	International Conference on Harmonisation
IP	Investigational Product
IPF	Inventory of Psychosocial Functioning
IR	Independent Rater
IRB	Institutional Review Board
ISF	Investigator Site File
ITT	Intent-to-Treat
IUD	Intrauterine Device
IUS	Intrauterine Hormone-releasing System
kg	Kilogram
LEC-5	Life Events Checklist
LTFU	Long-term Follow-up
MAPS	Multidisciplinary Association for Psychedelic Studies
MAOI	Monoamine Oxidase Inhibitor
MCH	Mean Corpuscular Hemoglobin
MCHC	Mean Corpuscular Hemoglobin Concentration
MCV	Mean Corpuscular Volume
MDMA	3,4-methylenedioxymethamphetamine
MedDRA	Medical Dictionary for Regulatory Activities
mg	Milligram
mITT	Modified Intent-to-Treat
mmHg	Milligrams of Mercury
MMRM	Mixed Model Repeated Measure
MPBC	MAPS Public Benefit Corporation
ms	Millisecond
PCL-5	PTSD Checklist for DSM-5
PTCA	Percutaneous Transluminal Coronary Angioplasty
PTSD	Posttraumatic Stress Disorder
RACT	Risk Assessment and Categorization Tool
RBC	Red Blood Cell
RDW	Red Cell Distribution Width
SAE	Serious Adverse Event
SCID-5-PD	Structured Clinical Interview for DSM-5 Personality Disorders
SCID-5-SPQ	SCID-5 Self-report Personality Questionnaire
SCS	Self-compassion Scale
SDS	Sheehan Disability Scale
SGOT	Serum Glutamic Oxaloacetic Transaminase
SNRI	Serotonin-norepinephrine Reuptake Inhibitor
SPGT	Serum Glutamic Pyruvic Transaminase
SRNU	Self-reported Nicotine Use
SSR	Sample size re-estimation
SSRI	Selective serotonin reuptake inhibitor
SUBJID	Subject Identifier
TAS-20	Toronto Alexithymia Scale
TEAE	Treatment Emergent Adverse Event
TSH	Thyroid-stimulating Hormone
UFEC	Utilization of Facility-based and Emergent Care
VA	U.S. Department of Veterans Affairs
VAS	Visual Analog Scale

WBCWhite Blood CellWHOWorld Health OrganizationWHO DDEWHO Drug Dictionary EnhancedTM

1.0 Definitions of Terms

Categorical data: refers to discrete (indivisible) variables, such as gender or ethnicity; data will be presented as total numbers of each category as needed to describe the sample

Completers: are defined as participants who complete all two planned experimental sessions and the CAPS-5 outcome assessment 14 weeks after enrollment (Visit 14).

Descriptive data: includes mean, median, standard deviation, minimum, and maximum of numerical data used as needed to describe the sample

Difference scores: consist of scores computed by subtracting one value from another, as subtracting Baseline from follow-up score, used to test for differences between and within groups to determine change as a function of experimental treatment over time

Dropouts: are defined as participants who withdraw consent due to any reason after dosing and no longer participate in the study, i.e. no further contact with investigators or site staff.

Effectiveness: type of analysis used to assess therapeutic effects or benefits

Exploratory analyses: inferential or descriptive analysis of the data to determine trends that might lead to hypotheses for further study

Frequency listing: tabular listing of numbers and/or percentages of events used as needed to describe the sample or data characteristics

Outcome measures: primary and secondary study measures that are used to test the study hypotheses

Post-dosing Early Terminators: are defined as participants who discontinue study treatment but continue to participate in study evaluations and outcome assessments.

Pre-dosing Early Terminators: are defined as participants who discontinue participation after enrollment but before randomization during the Preparatory Period and never receive study drug.

Process measures: study measures or qualitative observations collected during the study that may increase depth of understanding of the condition and treatment, although not necessarily related to safety or effectiveness

Protocol deviation: event that represents significant divergence from the intended study design as described in the protocol

Safety: assessment of indicators of potential risks and adverse events

Safety measures: study measures that assess safety of the Investigational Product (IP), such as heart rate monitoring, blood pressure, body temperature

Study design: all elements of a research project that define the study question, experimental methods, study procedures including enrollment, measurement techniques, data workflow, and statistical analysis

Tabular listing: list of each variable or item for each individual participant either in total or by treatment group in a table format

2.0 Introduction

This document contains a Statistical Analysis Plan (SAP) for an open-label study (MP18), "An Open-Label, Phase 2, Multicenter Feasibility Study of Manualized MDMA-Assisted Psychotherapy with an Optional fMRI Sub-Study Assessing Changes in Brain Activity in Subjects with Posttraumatic Stress Disorder." A separate SAP for the Optional fMRI Sub-Study is to be prepared.

This study is similar in study design, objectives, and protocols to MP16 and MP17, which are open-label three-session studies. The differences are the number of sessions (2 sessions in MP18, 3 sessions in MP16 and MP17), the number of subjects enrolled in each study, location of sites (MP18 at EU sites, MP16 at USA and MP17 at Canada sites) and the source and dose of MDMA. MDMA used in all studies have similar purity and drug properties. MP18 tests a flexible dosing regimen of 80mg MDMA in Session 1, and 80mg or 120mg MDMA in Sessions 2, each followed by a supplemental half-dose. MP16 tests a flexible dosing regimen of 80 mg MDMA in Sessions 2 and 3, each followed by a supplemental half-dose. MP17 tests a flexible dosing regimen of 100mg MDMA in Session 1, and 100mg or 120mg MDMA in Sessions 2 and 3, each followed by a supplemental half-dose.

The Multidisciplinary Association for Psychedelic Studies (MAPS) is a non-profit research and educational organization working to obtain approval for the prescription use of 3,4methylenedioxymethamphetamine (MDMA) in conjunction with psychotherapy in persons with posttraumatic stress disorder (PTSD). MAPS Europe B.V. has delegated statistical analysis to MAPS Public Benefit Corporation (MPBC).

The open-label Phase 2 MP18 study will serve as the lead-in to the sponsor's planned Phase 3 study in the European Economic Area (EEA). Only sites planned for Phase 3 will participate in these studies. These open-label lead-in Phase 2 studies will serve to validate assumptions made for statistical power calculations supporting planned Phase 3 clinical trials and will provide crosscultural verification data on the updated version of the instrument for the Primary Outcome measure, the Clinician Administered PTSD Scale for DSM-5 (CAPS-5), which will be used in Phase 3. In addition, these studies will gather supportive data on the safety and effect of manualized MDMA-assisted psychotherapy while providing an opportunity for clinical supervision to planned Phase 3 therapy teams. These studies will explore reproducibility of findings in a multi-site format to confirm the Phase 3 study design in the EEA region.

3.0 Study Objectives

3.1 Primary Objective

The primary objective of this study is to evaluate the effectiveness of MDMA-assisted psychotherapy for treatment of PTSD, as measured by the estimand of change in CAPS-5 Total Severity Score from Baseline (Visit 3) to 13 weeks post Baseline (Visit 14).

3.2 Secondary Objective

The secondary objective is to evaluate the effectiveness of MDMA-assisted psychotherapy for PTSD in clinician-rated functional impairment, as measured by the mean change in Sheehan Disability Scale (SDS) item scores from Visit 3 (Baseline) to Visit 14 (13 weeks post Baseline).

3.3 Safety Objectives

The overall safety objective is to assess severity, incidence and frequency of AEs, AEs of Special Interest (AESIs), and Serious Adverse Events (SAEs), concomitant medication use, suicidal ideation and behavior, and vital signs to support the package insert for MDMA-assisted psychotherapy. The following safety objectives will evaluate the safety of MDMA-assisted psychotherapy:

- 1. Assess incidence of AEs during Experimental Sessions that may be indicative of a medical complication of the Investigational Product (IP), such as clinical signs and symptoms of chest pain, shortness of breath, or neurological symptoms or any other signs or symptoms that prompt additional vital sign measurements.
- 2. Assess incidence of AEs by severity.
- 3. Assess incidence of Treatment Emergent AEs (TEAEs) by severity.
- 4. Assess incidence of TEAEs by severity taken during an Experimental Session and through 2 days after IP administration.
- 5. Assess incidence of AESIs, defined as AEs specified in he protocol related to cardiac function and abuse liability.
- 6. Assess incidence of AEs by severity categorized as leading to discontinuation of IP, resulting in death or hospitalization, and continuing at Study Termination.
- 7. Assess incidence of SAEs.
- 8. Assessincidence of psychiatric concomitant medications taken during an Experimental Session and through 2 days after IP administration.
- 9. Assess incidence of any psychiatric concomitant medications taken during the Treatment Period.
- 10. Assess incidence of serious suicidal ideation and positive suicidal behavior assessed with the Columbia Suicide Severity Rating Scale (C-SSRS).
- 11. Assess mean changes in blood pressure, heart rate, and body temperature from pre-IP administration to end of each Experimental Session.

